## SAFETY ENDPOINTS

	e-CIG VS. IQOS Statistical Analysis Plan Version 2.0	Doc code: BIOSTAT.SAP.02
		Pag. 63 of 115

Sponsor: Center for Tobacco Research, Cessation and Prevention, [name]  
Protocol: Progetto e-cig vs IQOS

Table S.1 Summary of Extent of Exposure by group  
Population: Safety

		Group HnB	Group EC
		N=XXX	N=XXX
Extent of Exposure	N	XX	XX
	N missing	XX	XX
	Mean	XX.X	XX.X
	Std. deviation	XX.X	XX.X
	Median	XX.X	XX.X
	Q1-Q3	XX.X - XX.X	XX.X - XX.X

---

<File: [..]\Work\_In\_Progress\[..]\Statistica\Programmi\xxxxx.sas>  
<Source: [..]\Work\_In\_Progress\[..]\Gestione Dati\Dati SAS\xxxxx.sas7bdat>      Generated on XXXXXXXXXX XX:XX  
The Extent of exposure is computed as (Visit 6 date - Baseline date)  
For further information see Listing X.X

	e-CIG VS. IQOS Statistical Analysis Plan Version 2.0	Doc code: BIOSTAT.SAP.02
		Pag. 64 of 115

Sponsor: Center for Tobacco Research, Cessation and Prevention, [name]  
Protocol: Progetto e-cig vs IQOS

Table S.2 Summary of Adverse Drug Reactions by group  
Population: Safety

	Group HnB N=XXX	Group EC N=XXX
ADRs	XX (XX.X%)	XX (XX.X%)
SADRs	XX (XX.X%)	XX (XX.X%)
Related ADRs	XX (XX.X%)	XX (XX.X%)

<File: [..]\Work\_In\_Progress\[..]\Statistica\Programmi\xxxxx.sas>  
<Source: [..]\Work\_In\_Progress\[..]\Gestione Dati\Dati SAS\xxxxx.sas7bdat>

Generated on XXXXXXXXXX XX:XX

The percentages are calculated on the total of the enrolled patients by group  
ADRS classified as Possible/Probably/Definite are considered as Related ADRS  
For further information see Listing X.X

e-CIG VS. IQOS  
Statistical Analysis Plan  
Version 2.0

Doc code:  
BIOSTAT.SAP.02

Pag. 65 of 115

Sponsor: Center for Tobacco Research, Cessation and Prevention, [name]  
Protocol: Progetto e-cig vs IQOS

Table S.3 Summary of Vital Signs by group < Group HnB / Group EC >  
Population: <Safety/Continuous Quitters>

Parameter <Unit>	Visit	Observed Values at Visit							Changes From Visit 1 to Visits 6 and 7						
		N	N miss	Mean	STD	CI 95%	Median	Range (Q1-Q3)	N	N miss	Mean	STD	CI 95%	Median	Range (Q1-Q3)
parameter #1 <um>	Baseline	XX	XX	XX.XX	XX.XX	[XX.XX,XXX.X]	XX.XX	(XX.XX - XXX.X)							
	Visit 2	XX	XX	XX.XX	XX.XX	[XX.XX,XXX.X]	XX.XX	(XX.XX - XXX.X)							
	. . . . . Follow-up	XX	XX	XX.XX	XX.XX	[XX.XX,XXX.X]	XX.XX	(XX.XX - XXX.X)	XX	XX	XX.XX	XX.XX	[XX.XX,XXX.X]	XX.XX	(XX.XX - XXX.X)
parameter #2 <um>	Baseline	XX	XX	XX.XX	XX.XX	[XX.XX,XXX.X]	XX.XX	(XX.XX - XXX.X)							
	Visit 2	XX	XX	XX.XX	XX.XX	[XX.XX,XXX.X]	XX.XX	(XX.XX - XXX.X)							
	. . . . . Follow-up	XX	XX	XX.XX	XX.XX	[XX.XX,XXX.X]	XX.XX	(XX.XX - XXX.X)	XX	XX	XX.XX	XX.XX	[XX.XX,XXX.X]	XX.XX	(XX.XX - XXX.X)
. . . . .															
parameter #n <um>	Baseline	XX	XX	XX.XX	XX.XX	[XX.XX,XXX.X]	XX.XX	(XX.XX - XXX.X)							
	Visit 2	XX	XX	XX.XX	XX.XX	[XX.XX,XXX.X]	XX.XX	(XX.XX - XXX.X)							
	. . . . . Follow-up	XX	XX	XX.XX	XX.XX	[XX.XX,XXX.X]	XX.XX	(XX.XX - XXX.X)	XX	XX	XX.XX	XX.XX	[XX.XX,XXX.X]	XX.XX	(XX.XX - XXX.X)

Sponsor: Center for Tobacco Research, Cessation and Prevention, [name]  
Protocol: Progetto e-cig vs IQOS

Table S.4 Summary of End of Study Information by group  
Population: Safety

		Group HnB	Group EC
		N=XXXX	N=XXXX
Was the study completed	Yes	XX (XX.X%)	XX (XX.X%)
According to the	No	XX (XX.X%)	XX (XX.X%)
Protocol?			
Study duration (days)	N	XX	XX
	N missing	XX	XX
	Mean	XX.X	XX.X
	Std. deviation	XX.X	XX.X
	Median	XX.X	XX.X
	Q25-Q75	X.X - XX.X	X.X - XX.X
If no, specify (Reason)	Reason#1	XX (XX.X%)	XX (XX.X%)
	Reason#2	XX (XX.X%)	XX (XX.X%)
	. . . . .	. . . . .	. . . . .
	Reason#n	XX (XX.X%)	XX (XX.X%)

<File: [..]\Work\_In\_Progress\[..\]Statistica\Programmi\xxxxx.sas>

<Source: [..]\Work\_In\_Progress\[..\]Gestione Dati\Dati SAS\xxxxx.sas7bdat>

For further information see Listing X.X

Generated on XXXXXXXX XX:XX

e-CIG VS. IQOS  
Statistical Analysis Plan  
Version 1.1

Doc code:  
BIOSTAT.SAP.02

Pag. 67 of 115

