## 4 ANALYSIS POPULATIONS

In the study protocol the analysis populations were not defined.

As for the safety analyses

the **Safety population**, defined as all the subject who assumed at least one dose of the product, will be considered for the safety analyses.

As for the efficacy analyses

The **Intention-To-treat** population, defined as all the subjects who assumed at least one dose of the study product and had at least one observation after the baseline, will be considered for all the other analyses.

The **Per-Protocol** population, defined as all the subjects that completed all the visits.

The **Per-Protocol V7** population (see DRM Minute in Appendix 5), defined as all the subjects that completed all the visits, included the Follow-up visit (Visit 7).

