## 8 STATISTICAL ANALYSES OF SAFETY ENDPOINTS

The Safety will be evaluated on all the subjects in the study through the analysis of the Adverse Events (AEs), i.e. those events, occurred during the study, which could be related or not related with the devices, and the Vital Signs.

No methods for replacing missing values will be applied. The Safety population will be considered for this analysis, therefore all the listings will be built with reference to the full set of enrolled patients. As for the Vital Signs, a further analysis in the subpopulation of the “Continuous Quitter” will be presented.

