### 8.1 Extent of Exposure and study duration

The study duration (from Baseline to last Visit) will be summarized in Table S.1 and listed in term of baseline date, final visit date and time interval in days in Listing S.1.

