### 8.4 End study information

Table S.4 (Appendix 2) will include all the information recorded in the End Study Form of the eCRF, i.e. completeness of the study and frequency table of the reasons for the study interruption. As for the study duration (variable "End Study Date") the analysis will be presented in Table S.1 (see Section 9.1). The data will also be listed in Listing S.3 (Appendix 3).

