## 9.7 Decision taken during the DRM

As described in the Minute included in Appendix 5, on the 10th June 2020 the Data Review Meeting of the study was held in call conference manner. All the decision taken were reported in the Minute. The main decision regarded the analysis population definition. All the protocol violations were evaluated, therefore the following populations were approved by the team:

Population **Safety**: 220

	e-CIG VS. IQOS Statistical Analysis Plan Version 2.0	Doc code: BIOSTAT.SAP.02
		Pag. 21 of 115

Population **Intention-To-Treat**: 217

Population **Per-Protocol**: 193

Population **Per-Protocol V7**: 177

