**3 – Uscita prematura dallo studio**

Per definizione, tutti i soggetti “drop-out” a Visita 6 sono da ritenersi violatori MAGGIORI. Tutti i soggetti che escono dallo studio dopo Visita 2 sono stati esclusi solo dalla popolazione Per-Protocol. I soggetti che escono dallo studio dopo Visita 1 sono stati esclusi anche dalla popolazione ITT.

Nalla call del 22 Giugno è stato deciso di considerare una seconda popolazione PP, la “Per-Protocol V7”, composta da tutti i soggetti, non violatori, che completano anche la visita di follow-up (Visita 7).

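### Table S.1 computes exposure to Visit 6 with no fallback, so subjects without a Visit 6 date get no value, while SAP 8.1 and 8.4 send a different interval to the same table

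*SAP*

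**What the plan says.** The Table S.1 shell (SAP Appendix 2, Safety Endpoints) is labelled for the Safety population and has one variable, extent of exposure, with rows for N, N missing, mean, SD, median and quartiles. Its footnote gives the rule: "The Extent of exposure is computed as (Visit 6 date - Baseline date".

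Other parts of the SAP bear on the same table:

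- **Section 4** makes the Safety population everyone "defined as all the subject who assumed at least one dose of the product", so it includes early leavers.
- **Section 8** states for the safety analyses: "No methods for replacing missing values will be applied".
- **Section 8.1** says: "The study duration (from Baseline to last Visit) will be summarized in Table S.1". The data are to be "listed in term of baseline date, final visit date and time interval in days in Listing S.1".
- **Section 8.4** says of study duration, taken from the End Study Date, that "the analysis will be presented in Table S.1".
- **The Listing S.1 shell** (Appendix 3) has a start date, an end date and a column headed Days of Exposure.
- **Appendix 1** gives the title of Table S.1 as exposure and compliance. The shell has no compliance row.
- **Table S.4** already has a row for study duration in days, in the Safety population.

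The Data Review Meeting (DRM) minute in Appendix 5 confirms that subjects left early. Drop-outs at Visit 6 "sono da ritenersi violatori MAGGIORI" (count as major violators). Those who left after Visit 1 are also outside the ITT population.

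**The concern.** The formula cannot be evaluated for part of the population in the table's own title. Subjects without a Visit 6 date drop out of the mean, median and quartiles, and those who left early are the subjects with the shortest time in the treatment period. Leaving them out can only raise the summary. A table headed Safety would in effect describe Visit 6 attenders.

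The SAP also gives one table two different intervals. A programmer who follows the footnote ends at Visit 6. One who follows 8.1 or 8.4 ends at the last visit or the End Study Date, which for a subject seen at follow-up is about 12 weeks later. The table and the listing that supports it could then show different numbers of days for the same subject.

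At stake is the description of how long subjects were followed on their allocated product. That is context for the adverse event tables and not an input to them.

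**Working it through.** The plan gives no expected mean exposure, so there is no stated figure to reproduce.

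**Inputs.** The population sizes come from SAP 9.7: Safety 220, ITT 217, "Population Per-Protocol: 193" and Per-Protocol V7 177. The nominal visit days come from the protocol visit schedule: Visit 6 at week 12 = 12 × 7 = day 84, and Visit 7 at week 24 = 24 × 7 = day 168, each with a window of 7 days either way.

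**How many subjects lack a value.** Per-Protocol requires all visits to be completed, so nobody without a Visit 6 can be in it.

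- Upper bound: 220 − 193 = 27, and 27/220 = 12.3%. The remaining 193/220 = 87.7% contribute.
- Lower bound: ITT requires at least one observation after baseline, so the 220 − 217 = 3 subjects outside it have no Visit 6. 3/220 = 1.4%.
- The other 217 − 193 = 24 are in ITT but not in Per-Protocol. The documents do not show how many of these reached Visit 6.

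**Effect on the mean.** Under the footnote, the mean over subjects with a Visit 6 date is nominally 84 days. With the interval ended at the last visit and capped at Visit 6, all 220 contribute. Assume that the 3 left at day 0 and that the 24 had a last visit on day *x*:

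mean = (193 × 84 + 3 × 0 + 24 × *x*) / 220

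| *x* (assumed) | Numerator | Mean, all 220 |
|---|---|---|
| 7 | 16,212 + 168 = 16,380 | 74.5 days |
| 28 | 16,212 + 672 = 16,884 | 76.7 days |
| 56 | 16,212 + 1,344 = 17,556 | 79.8 days |

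The overstatement is then 84 − 79.8 = 4.2 to 84 − 74.5 = 9.5 days. If instead all 24 did attend Visit 6, the mean is 217 × 84 / 220 = 82.9 days and the overstatement is about 1.1 days.

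**The two intervals.** For a subject who attended Visit 7, the footnote gives nominally 84 days and baseline to last visit gives 168. This applies to the 177 in Per-Protocol V7, not to all 193 in Per-Protocol.

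**The case against.** Several points on the other side stand.

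- **Study duration is not exposure.** A reader might infer that 8.1 counts the 12 weeks after free supply ended as exposure and so doubles it. The text does not say that. 8.1 defines study duration, its heading names the two quantities separately, and the only exposure formula is the footnote, which stops when supply stops. What remains is a mismatch of layout and labels: duration is sent to a table with no row for it, and Listing S.1 calls its interval exposure.
- **Study duration is reported.** Table S.4 has the row. The text of 8.1 and 8.4 points to the wrong table.
- **Days of use are analysed.** SAP 7.2.2 and the DRM minute relate diary days of use to study days, in the minute from Visit 1 to Visit 6. The result goes to Table E.3 for ITT and Per-Protocol, though not for Safety.
- **The gap would show.** The N missing row tells the reader how many subjects are absent. It does not correct the mean.
- **No adverse event rate depends on exposure.** Adverse events are numbers and percentages of subjects, and no exposure-adjusted rate is planned. It is tempting to say that event incidence is misread, but no planned figure changes.
- **27 is a ceiling.** A missed intermediate visit also excludes a subject from Per-Protocol, and other exclusions are possible. Under the protocol's Discontinuation Criteria, subjects who stop the product may keep the visit schedule and so have a Visit 6 date. The protocol also requires a final evaluation at discontinuation. If sites entered it as Visit 6, fewer values are missing, but no document says so.

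None of this supplies a fallback end date for a Safety subject without a Visit 6 date.

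**Conclusion.** The rule in the Table S.1 footnote is wrong as written for a Safety-population table. It gives no value to subjects without a Visit 6 date, at least 3 and at most 27 of 220 (1.4% to 12.3%), and its mean describes only those who reached Visit 6. With the stated assumptions about exit times, the all-subject mean is about 74.5 to 79.8 days against a nominal 84. No single figure in that range can be called the true mean: the exit times are not in the documents, and a visit interval is not the same as days of product use.

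Sections 8.1 and 8.4 disagree with the shell about what Table S.1 contains, and the Listing S.1 label adds to the confusion.

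The consequence is small. Adverse event percentages and the primary endpoint do not change. A reader might infer a biased comparison of exposure between arms, but no counts by arm are given, so neither its presence nor its direction can be judged.

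**What to change.** 1. Define extent of exposure for all 220 Safety subjects as the earlier of the Visit 6 date and the last visit or discontinuation date, minus the baseline date. State that for a subject who missed Visit 6 but attended Visit 7, the last visit attended before Visit 6 is used, so that the cap holds.
2. Report study duration only in Table S.4, where the row exists, and change 8.1 and 8.4 to point there. The reference in 8.4 to section 9.1 for Table S.1 should be corrected at the same time.
3. Use the same definition in the Table S.1 footnote and in Listing S.1. Either reserve the Days of Exposure column for the capped interval or add a separate duration column.
4. Settle the title of Table S.1: remove compliance from the Appendix 1 title or add the row.
5. Optionally, show diary days of use for the Safety population beside the interval.

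The cost is one derived variable from dates already in the database, plus edits to two sections, a footnote, a title and a listing. No new data are needed.

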**APPENDIX 3**  
**Mock tables: Listings**

	e-CIG VS. IQOS Statistical Analysis Plan Version 1.1	Doc code: BIOSTAT.SAP.02
		Pag. 68 of 115

## **BASELINE CHARACTERISTICS**

Sponsor: Center for Tobacco Research, Cessation and Prevention, [name]  
Protocol: Progetto e-cig vs IQOS

Listing D.1 Patients' Disposition

Screening Number	Random. Number	Age/Gender	Enroled (Y/N)	Completed (Y/N)
XXXXX	XXXXX	XX/XXXX	X	X
XXXXX	XXXXX	XX/XXXX	X	X
XXXXX	XXXXX	XX/XXXX	X	X
XXXXX	XXXXX	XX/XXXX	X	X
XXXXX	XXXXX	XX/XXXX	X	X
XXXXX	XXXXX	XX/XXXX	X	X
XXXXX	XXXXX	XX/XXXX	X	X
XXXXX	XXXXX	XX/XXXX	X	X
XXXXX	XXXXX	XX/XXXX	X	X
XXXXX	XXXXX	XX/XXXX	X	X
XXXXX	XXXXX	XX/XXXX	X	X

Sponsor: Center for Tobacco Research, Cessation and Prevention, [name]  
Protocol: Progetto e-cig vs IQOS

Listing D.2 Eligibility: Inclusion Criteria < Group HnB / Group EC >

Screening Number	Random. Number	Age/Gender	Inclusion Crit. #1	Inclusion Crit. #2	Inclusion Crit. #3	Inclusion Crit. #4	Inclusion Crit. #5	Inclusion Crit. #6
XXXXXX	XXXXXX	XX/XXXX	X	X	X	X	X	X
XXXXXX	XXXXXX	XX/XXXX	X	X	X	X	X	X
XXXXXX	XXXXXX	XX/XXXX	X	X	X	X	X	X
XXXXXX	XXXXXX	XX/XXXX	X	X	X	X	X	X
XXXXXX	XXXXXX	XX/XXXX	X	X	X	X	X	X
XXXXXX	XXXXXX	XX/XXXX	X	X	X	X	X	X
XXXXXX	XXXXXX	XX/XXXX	X	X	X	X	X	X

<File: [..]\Work\_In\_Progress\[..]\Statistica\Programmi\xxxxx.sas>

<Source: [..]\Work\_In\_Progress\[..]\Gestione Dati\Dati SAS\xxxxx.sas7bdat>      Generated on XXXXXXXXXX XX:XX

Incl.Crit.#1: Able to comply with study procedures.

Incl.Crit.#2: Male or female healthy smokers aged ≥19.

Incl.Crit.#3: Smoking at least 10 cigarettes a day.

Incl.Crit.#4: Smoking for at least one year.

Incl.Crit.#5: Not currently attempting to quit smoking or wishing to do so in the next 30 days (this will be verified at screening by the answer ``NO`` to both questions ``Do you intend to quit in the next 30 days?`` and ``Are you interested in taking part in one of our smoking cessation programs?``).

Incl.Crit.#6: Female smokers not planning to become pregnant are using an acceptable form of contraception.

<Ordered by: Screening Number>

<Stratified by: Group>

Sponsor: Center for Tobacco Research, Cessation and Prevention, [name]  
Protocol: Progetto e-cig vs IQOS

Listing D.3 Eligibility: Exclusion Criteria <Group HnB / Group EC >

Screening Number	Random. Number	Age/Gender	Exclusion Crit. #1	Exclusion Crit. #2	Exclusion Crit. #3	Exclusion Crit. #4
XXXXXX	XXXXXX	XX/XXXX	X	X	X	X
XXXXXX	XXXXXX	XX/XXXX	X	X	X	X
XXXXXX	XXXXXX	XX/XXXX	X	X	X	X
XXXXXX	XXXXXX	XX/XXXX	X	X	X	X
XXXXXX	XXXXXX	XX/XXXX	X	X	X	X
XXXXXX	XXXXXX	XX/XXXX	X	X	X	X
XXXXXX	XXXXXX	XX/XXXX	X	X	X	X

<File: [..]\Work\_In\_Progress\[..]\Statistica\Programmi\xxxxx.sas>

<Source: [..]\Work\_In\_Progress\[..]\Gestione Dati\Dati SAS\xxxxx.sas7bdat>

Generated on XXXXXXXX XX:XX

Excl.Crit.#1: Use of smokeless tobacco, or any other tobacco products (including e-cigarettes, cigars, chewing tobacco, snus, etc.) within the last 3 months, at baseline and during the whole study;

Excl.Crit.#2: Use of nicotine replacement therapy or other smoking cessation therapies within the last 3 months and at baseline;

Excl.Crit.#3: Self-reported pregnancy, planned pregnancy or breastfeeding;

Excl.Crit.#4: Tobacco industry employees and 1st degree relatives will be excluded in order to safeguard independence of the study.

<Ordered by: Screening Number>

<Stratified by: Group>

Sponsor: Center for Tobacco Research, Cessation and Prevention, [name]  
Protocol: Progetto e-cig vs IQOS

Listing D.4b Smoking information < Group HnB / Group EC >

Screening Number	Random. Number	Age/Gender	How long smoked at least 10 cigarettes/die (years)	Brand of used cigarettes	Years of smoking	Number of quit attempts	Visit	Number of cigarette/die	Exhaled breath Carbon monoxide
XXXXXX	XXXXXX	XX/XXXX	XX	XXXXXXXXXX	XX	XX	XXXXXX XXXXXX XXXXXX XXXXXX XXXXXX XXXXXX XXXXXX	XX XX XX XX XX XX XX	XXX XXX XXX XXX XXX XXX XXX
XXXXXX	XXXXXX	XX/XXXX	XX	XXXXXXXXXX	XX	XX	XXXXXX XXXXXX XXXXXX XXXXXX XXXXXX XXXXXX XXXXXX	XX XX XX XX XX XX XX	XXX XXX XXX XXX XXX XXX XXX
XXXXXX	XXXXXX	XX/XXXX	XX	XXXXXXXXXX	XX	XX	XXXXXX XXXXXX XXXXXX XXXXXX XXXXXX XXXXXX XXXXXX	XX XX XX XX XX XX XX	XXX XXX XXX XXX XXX XXX XXX

---

<File: [..]\Work\_In\_Progress\[..]\Statistica\Programmi\xxxxx.sas>  
<Source: [..]\Work\_In\_Progress\[..]\Gestione Dati\Dati SAS\xxxxx.sas7bdat>      Generated on XXXXXXXXXX XX:XX

<Ordered by: Screening Number>  
<Stratified by: Group>

Sponsor: Center for Tobacco Research, Cessation and Prevention, [name]  
 Protocol: Progetto e-cig vs IQOS

Listing D.5 Past and Present Medical History < Group HnB / Group EC >

Screening Number	Random. Number	Age/Gender	Date of Visit	Description	Date of Onset	Date Resolved	Ongoing (Y/N)	Comment
XXXXXX	XXXXXX	XX/XXXX	XX/XX/XXXX	XXXXXXXXXX	XX/XX/XXXX	XX/XX/XXXX	X	XXXXXXXXXX
XXXXXX	XXXXXX	XX/XXXX	XX/XX/XXXX	XXXXXXXXXX	XX/XX/XXXX	XX/XX/XXXX	X	XXXXXXXXXX
XXXXXX	XXXXXX	XX/XXXX	XX/XX/XXXX	XXXXXXXXXX	XX/XX/XXXX	XX/XX/XXXX	X	XXXXXXXXXX
XXXXXX	XXXXXX	XX/XXXX	XX/XX/XXXX	XXXXXXXXXX	XX/XX/XXXX	XX/XX/XXXX	X	XXXXXXXXXX
XXXXXX	XXXXXX	XX/XXXX	XX/XX/XXXX	XXXXXXXXXX	XX/XX/XXXX	XX/XX/XXXX	X	XXXXXXXXXX
XXXXXX	XXXXXX	XX/XXXX	XX/XX/XXXX	XXXXXXXXXX	XX/XX/XXXX	XX/XX/XXXX	X	XXXXXXXXXX
XXXXXX	XXXXXX	XX/XXXX	XX/XX/XXXX	XXXXXXXXXX	XX/XX/XXXX	XX/XX/XXXX	X	XXXXXXXXXX
XXXXXX	XXXXXX	XX/XXXX	XX/XX/XXXX	XXXXXXXXXX	XX/XX/XXXX	XX/XX/XXXX	X	XXXXXXXXXX
XXXXXX	XXXXXX	XX/XXXX	XX/XX/XXXX	XXXXXXXXXX	XX/XX/XXXX	XX/XX/XXXX	X	XXXXXXXXXX
XXXXXX	XXXXXX	XX/XXXX	XX/XX/XXXX	XXXXXXXXXX	XX/XX/XXXX	XX/XX/XXXX	X	XXXXXXXXXX

Sponsor: Center for Tobacco Research, Cessation and Prevention, [name]  
 Protocol: Progetto e-cig vs IQOS

Listing D.6 Urine Collection and Storage < Group HnB / Group EC >

Screening Number	Random. Number	Age/Sex	Instruction given to the subject?	No. of urine Containers delivered	Visit	Has the subject returned the urine to the center?
XXXXXX	XXXXXX	XX.X/XXXX	XXX	XXX	XXXXXXX	
				XXX	XXXXXXX	XXX
					XXXXXXX	XXX
XXXXXX	XXXXXX	XX.X/XXXX	XXX	XXX	XXXXXXX	
				XXX	XXXXXXX	XXX
					XXXXXXX	XXX
XXXXXX	XXXXXX	XX.X/XXXX	XXX	XXX	XXXXXXX	
				XXX	XXXXXXX	XXX
					XXXXXXX	XXX
XXXXXX	XXXXXX	XX.X/XXXX	XXX	XXX	XXXXXXX	
				XXX	XXXXXXX	XXX
					XXXXXXX	XXX

<File: [..]\Work\_In\_Progress\[..]\Statistica\Programmi\xxxxx.sas>  
 <Source: [..]\Work\_In\_Progress\[..]\Gestione Dati\Dati SAS\xxxxx.satd7sas> Generated on XXXXXXXX XX:XX

<Ordered by: Screening Number>  
 <Stratified by: Group>

Sponsor: Center for Tobacco Research, Cessation and Prevention, [name]  
Protocol: Progetto e-cig vs IQOS

Listing D.7 Fagerstrom test for nicotine dependance < Group HnB / Group EC >

Screening Number	Random. Number	Visit	Age/Gender	Q1	Q2	Q3	Q4	Q5	Q6
XXXXXX	XXXXXX	XXXXXX	XX/XXXX	XXXXX	XXXXX	XXXXX	XXXXX	XXXXX	XXXXX
XXXXXX	XXXXXX	XXXXXX	XX/XXXX	XXXXX	XXXXX	XXXXX	XXXXX	XXXXX	XXXXX
XXXXXX	XXXXXX	XXXXXX	XX/XXXX	XXXXX	XXXXX	XXXXX	XXXXX	XXXXX	XXXXX
XXXXXX	XXXXXX	XXXXXX	XX/XXXX	XXXXX	XXXXX	XXXXX	XXXXX	XXXXX	XXXXX
XXXXXX	XXXXXX	XXXXXX	XX/XXXX	XXXXX	XXXXX	XXXXX	XXXXX	XXXXX	XXXXX
XXXXXX	XXXXXX	XXXXXX	XX/XXXX	XXXXX	XXXXX	XXXXX	XXXXX	XXXXX	XXXXX
XXXXXX	XXXXXX	XXXXXX	XX/XXXX	XXXXX	XXXXX	XXXXX	XXXXX	XXXXX	XXXXX

<File: [..]\Work\_In\_Progress\[..]\Statistica\Programmi\xxxxx.sas>  
<Source: [..]\Work\_In\_Progress\[..]\Gestione Dati\Dati SAS\xxxxx.sas7bdat>      Generated on XXXXXXXXXX XX:XX

- Q1: Quanto tempo dopo il risveglio fuma la prima sigaretta?
- Q2: Trova difficile non fumare nei luoghi dove è vietato?
- Q3: A quale sigaretta farebbe più fatica a rinunciare?
- Q4: Quante sigarette fuma al giorno?
- Q5: Tende a fumare più spesso nelle prime ore dopo il risveglio che durante il resto del giorno?
- Q6: Fuma anche se è malato e deve rimanere a letto la maggior parte del giorno?

<Ordered by: Screening Number>  
<Stratified by: Group>

Sponsor: Center for Tobacco Research, Cessation and Prevention, [name]  
 Protocol: Progetto e-cig vs IQOS

Listing D.8 Step Test < Group HnB / Group EC >

Screening Number	Ranom. Number	Age/Gender	Visit	Basale HR	SpO2	Step 1 HR	SpO2	Step 2 HR	SpO2	Step 3 HR	SpO2	Step 4 HR	SpO2	Step 5 HR	SpO2	Recovery HR	SpO2	Stop Time	V02MAX
XXXXXX	XXXXXX	XX.X/XXXX	XXXXXXXX	XX.X	XX.X	XX.X	XX.X	XX.X	XX.X	XX.X	XX.X	XX.X	XX.X	XX.X	XX.X	XX.X	XX.X	XXXX	XX.XX
			XXXXXXXX	XX.X	XX.X	XX.X	XX.X	XX.X	XX.X	XX.X	XX.X	XX.X	XX.X	XX.X	XX.X	XX.X	XX.X	XXXX	XX.XX
			XXXXXXXX	XX.X	XX.X	XX.X	XX.X	XX.X	XX.X	XX.X	XX.X	XX.X	XX.X	XX.X	XX.X	XX.X	XX.X	XXXX	XX.XX
			XXXXXXXX	XX.X	XX.X	XX.X	XX.X	XX.X	XX.X	XX.X	XX.X	XX.X	XX.X	XX.X	XX.X	XX.X	XX.X	XXXX	XX.XX
XXXXXX	XXXXXX	XX.X/XXXX	XXXXXXXX	XX.X	XX.X	XX.X	XX.X	XX.X	XX.X	XX.X	XX.X	XX.X	XX.X	XX.X	XX.X	XX.X	XX.X	XXXX	XX.XX
			XXXXXXXX	XX.X	XX.X	XX.X	XX.X	XX.X	XX.X	XX.X	XX.X	XX.X	XX.X	XX.X	XX.X	XX.X	XX.X	XXXX	XX.XX
			XXXXXXXX	XX.X	XX.X	XX.X	XX.X	XX.X	XX.X	XX.X	XX.X	XX.X	XX.X	XX.X	XX.X	XX.X	XX.X	XXXX	XX.XX
			XXXXXXXX	XX.X	XX.X	XX.X	XX.X	XX.X	XX.X	XX.X	XX.X	XX.X	XX.X	XX.X	XX.X	XX.X	XX.X	XXXX	XX.XX
XXXXXX	XXXXXX	XX.X/XXXX	XXXXXXXX	XX.X	XX.X	XX.X	XX.X	XX.X	XX.X	XX.X	XX.X	XX.X	XX.X	XX.X	XX.X	XX.X	XX.X	XXXX	XX.XX
			XXXXXXXX	XX.X	XX.X	XX.X	XX.X	XX.X	XX.X	XX.X	XX.X	XX.X	XX.X	XX.X	XX.X	XX.X	XX.X	XXXX	XX.XX
			XXXXXXXX	XX.X	XX.X	XX.X	XX.X	XX.X	XX.X	XX.X	XX.X	XX.X	XX.X	XX.X	XX.X	XX.X	XX.X	XXXX	XX.XX
			XXXXXXXX	XX.X	XX.X	XX.X	XX.X	XX.X	XX.X	XX.X	XX.X	XX.X	XX.X	XX.X	XX.X	XX.X	XX.X	XXXX	XX.XX

Sponsor: Center for Tobacco Research, Cessation and Prevention, [name]  
Protocol: Progetto e-cig vs IQOS

Listing D.9 Device consignment < Group HnB / Group EC >

Screening Number	Random. Number	Age/Gender	Visit	Has the device been tested and does it work?	Has the subject been trained for the allocated device?	<see > footnote>	<see footnote>
XXXXXX	XXXXXX	XX/XXXX	XXXXXX	XXX XXXXXX XXXXXX XXXXXX	XXXXXXXXXXXXX XXXXXXXXXXXXX XXXXXXXXXXXXX XXXXXXXXXXXXX	XXXXX XXXXX XXXXX XXXXX	XXXXXXXXXXXXX XXXXXXXXXXXXX XXXXXXXXXXXXX XXXXXXXXXXXXX
XXXXXX	XXXXXX	XX/XXXX	XXXXXX	XXX XXXXXX XXXXXX XXXXXX	XXXXXXXXXXXXX XXXXXXXXXXXXX XXXXXXXXXXXXX XXXXXXXXXXXXX	XXXXX XXXXX XXXXX XXXXX	XXXXXXXXXXXXX XXXXXXXXXXXXX XXXXXXXXXXXXX XXXXXXXXXXXXX
XXXXXX	XXXXXX	XX/XXXX	XXXXXX	XXX XXXXXX XXXXXX XXXXXX	XXXXXXXXXXXXX XXXXXXXXXXXXX XXXXXXXXXXXXX XXXXXXXXXXXXX	XXXXX XXXXX XXXXX XXXXX	XXXXXXXXXXXXX XXXXXXXXXXXXX XXXXXXXXXXXXX XXXXXXXXXXXXX
XXXXXX	XXXXXX	XX/XXXX	XXXXXX	XXX XXXXXX XXXXXX XXXXXX	XXXXXXXXXXXXX XXXXXXXXXXXXX XXXXXXXXXXXXX XXXXXXXXXXXXX	XXXXX XXXXX XXXXX XXXXX	XXXXXXXXXXXXX XXXXXXXXXXXXX XXXXXXXXXXXXX XXXXXXXXXXXXX

<File: [..]\Work\_In\_Progress\[..]\Statistica\Programmi\xxxxx.sas>  
<Source: [..]\Work\_In\_Progress\[..]\Gestione Dati\Dati SAS\xxxxx.sas7bdat>      Generated on XXXXXXXX XX:XX

<Ordered by: Screening Number>  
<Stratified by: Group>  
<No. of sticks delivered - Preferred flavor@of heatstick / Quantity in mg/ml of e-liquid bottles - Preferred flavor@of e-liquid>

Sponsor: Center for Tobacco Research, Cessation and Prevention, [name]  
Protocol: Progetto e-cig vs IQOS

Listing D.10 Device supply and accountability < Group HnB / Group EC >

Screening Number	Random. Number	Age/Gender	Visit	<see footnote>
XXXXXX	XXXXXX	XX/XXXX	XXXXXXX	XXX
			XXXXXXX	XXX
			XXXXXXX	XXX
			XXXXXXX	XXX
			XXXXXXX	XXX
XXXXXX	XXXXXX	XX/XXXX	XXXXXXX	XXX
			XXXXXXX	XXX
			XXXXXXX	XXX
			XXXXXXX	XXX
			XXXXXXX	XXX
XXXXXX	XXXXXX	XX/XXXX	XXXXXXX	XXX
			XXXXXXX	XXX
			XXXXXXX	XXX
			XXXXXXX	XXX
			XXXXXXX	XXX

<File: [..]\Work\_In\_Progress\[..]\Statistica\Programmi\xxxxx.sas>

<Source: [..]\Work\_In\_Progress\[..]\Gestione Dati\Dati SAS\xxxxx.sas7bdat>      Generated on XXXXXXXXXX XX:XX

<Ordered by: Screening Number>

<Stratified by: Group>

< Average sticks consumed per day / No. of empty e-liquid refill bottles returned>

Sponsor: Center for Tobacco Research, Cessation and Prevention, [name]  
Protocol: Progetto e-cig vs IQOS

Listing D.11 Product use recording < Group HnB / Group EC >

Screening Number	Random. Number	Age/Gender	Q1	If yes, specify type and amount of daily use	Q2	If yes, average <sticks/e-liquid in ml consumed> per day
XXXXXX	XXXXXX	XX/XXXX	XXX	XXXXXXXXXXXXXXXXXXXXXXXXXXXX	XXX	XXXXXXXXXX
XXXXXX	XXXXXX	XX/XXXX	XXX	XXXXXXXXXXXXXXXXXXXXXXXXXXXX	XXX	XXXXXXXXXX
XXXXXX	XXXXXX	XX/XXXX	XXX	XXXXXXXXXXXXXXXXXXXXXXXXXXXX	XXX	XXXXXXXXXX
XXXXXX	XXXXXX	XX/XXXX	XXX	XXXXXXXXXXXXXXXXXXXXXXXXXXXX	XXX	XXXXXXXXXX
XXXXXX	XXXXXX	XX/XXXX	XXX	XXXXXXXXXXXXXXXXXXXXXXXXXXXX	XXX	XXXXXXXXXX
XXXXXX	XXXXXX	XX/XXXX	XXX	XXXXXXXXXXXXXXXXXXXXXXXXXXXX	XXX	XXXXXXXXXX
XXXXXX	XXXXXX	XX/XXXX	XXX	XXXXXXXXXXXXXXXXXXXXXXXXXXXX	XXX	XXXXXXXXXX
XXXXXX	XXXXXX	XX/XXXX	XXX	XXXXXXXXXXXXXXXXXXXXXXXXXXXX	XXX	XXXXXXXXXX
XXXXXX	XXXXXX	XX/XXXX	XXX	XXXXXXXXXXXXXXXXXXXXXXXXXXXX	XXX	XXXXXXXXXX
XXXXXX	XXXXXX	XX/XXXX	XXX	XXXXXXXXXXXXXXXXXXXXXXXXXXXX	XXX	XXXXXXXXXX

<File: [..]\Work\_In\_Progress\[..]\Statistica\Programmi\xxxxx.sas>  
<Source: [..]\Work\_In\_Progress\[..]\Gestione Dati\Dati SAS\xxxxx.sas7bdat>      Generated on XXXXXXXX XX:XX

Q1: Did the subject use different RRP or other anti-smoking products during the last three months?  
Q2: If no, are you using the products delivered by this study?

<Ordered by: Screening Number>  
<Stratified by: Group>

	e-CIG VS. IQOS Statistical Analysis Plan Version 1.1	Doc code: BIOSTAT.SAP.02
		Pag. 81 of 115

